6.2. Screening Visit (-21 days before start of treatment)

Potentially eligible patients will be identified by chart review and treating physicians and offered an opportunity to provide informed consent. Screening laboratory, history and physical examination will be performed after subjects have provided written informed consent. Eligible subjects will be enrolled on study within 21 days of screening and subjects will begin vactosertib (DL1) within 28 days of screening. The following procedures will be performed within 28 days of starting the first dose of vactosertib (DL1):

6.2.1. Informed consent

Potentially eligible subjects will be identified by treating physician and written Informed Consent Obtained before any study-specific procedures are performed.

6.2.2. Once Informed Consent is provided, subjects will complete screening tests:

6.2.2.1. Screening Blood Studies

- CBC
- CMP, Uric Acid, Phosphorus and LDH
- Serum erythropoietin (EPO) level
- Cardiac troponin, BNP, and CK-MB
- Myeloid molecular panel by NGS

6.2.2.2. EKG

6.2.2.3. Transthoracic Echocardiogram

6.2.2.4. Abdominal Sonogram of upper left quadrant to record Spleen size

6.2.2.5. History and Physical Exam

6.2.2.6. Record palpated spleen size

6.2.2.7. Record ECOG performance status

6.2.2.8. Bone marrow aspirate (BMA) and biops

6.2.2.9. Collection of Research blood (20mL) and bone marrow specimens (for pSMAD and VAF quantification).

6.2.2.10. Recording of Transfusion History for the two months (8 weeks) prior to screening.

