4.2 Inclusion Criteria

- Age ≥ 18 years
- Patients meet the WHO 2016 criteria for a Ph-neg MPN (including PV, ET, MF, MDS/MPN, MPN-U).
- Patients with MF must have DIPSS+ Intermediate or High-risk MF (primary or post-PV/ET)
- Patients should be on a stable dose of current cytoreductive therapy for at least 3 months prior to C1D1.
- Anemia as defined by HGB < 10 g/dL, or transfusion of ≥ 2 packed red blood cell (PRBC) unit within the past 4 weeks with HGB ≤ 8.5g/dL. The anemia, in the investigator's opinion,

must be due to underlying MPN and not due to other causes such as the toxic effects of prior cytoreductive chemotherapy.

- Ineligible, unsuitable or refractoriness to ESA therapy defined as any of the following:
 - Serum erythropoietin (EPO) >125 U/L⁴.
 - Proven ESA unsuitability is defined by history of any of the following:
 - Loss of erythroid hematologic improvement while receiving stable or increased ESA dose; or
 - ESA-attributed toxicity that, in the treating physician's opinion, makes ESA therapy unsuitable for subject.
 - ESA refractoriness defined by lack of erythroid hematologic improvement to ESA:²⁷
 - Less than 1.5 g/dL increase in hemoglobin after at least 6 weeks of ESA therapy; or
 - Ongoing transfusion dependence that has not been reduced by >4 U over an 8-week period compared to ESA pre-treatment 8 weeks.
- ECOG Performance status ≤ 2
- Able to swallow tablets
- Able to give written informed consent
- Willing and able to comply with scheduled visits, treatment plans, tests and procedures.
- Acceptable Organ Function as defined by:
 - serum creatinine ≤ 2 mg/dL or > 50 mL/min/1.73m² by direct measure
 - AST(SGOT)/ALT(SGPT) ≤ 3 x institutional upper limit of normal
 - Total bilirubin ≤ 2 x institutional upper limit of normal

Note: Subjects with documented diagnosis of Gilbert's Syndrome resulting in elevated total bilirubin levels will be eligible provided all other eligibility criteria are met.

Note: Subjects with total bilirubin 2-3 mg/dL and direct (conjugated) bilirubin in the normal range will be eligible, provided all other eligibility criteria are met.

- Acceptable Cardiovascular status as defined by:
 - Mean QT interval corrected for heart rate using Fridericia's formula (QTcF) ≤ 450 ms for males, and ≤ 470 ms for females on screening ECG.

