6.1 Schedule of Assessments

Table 1a. Tier 1 schedule of trial events 6.1.1

Tier 1 Schedule of Assessments	Screening	Treatment Tier 1															
		Cycle 1				Cycle 2				Cycle 3				Cycle 4			
Pre-study D-28 to -1		Wk1 ^a	Wk2 ^a	Wk3 ^a	Wk4 ^a	Wk5 ^a	Wk6 ^a	Wk7 ^a	Wk8 ^a	Wk9 ^a	Wk10 ^a	Wk11 ^a	Wk12 ^a	Wk13 ^a	Wk14 ^a	Wk15 ^a	Wk16 ^a
Informed Consent Form	X																
Inclusion/Exclusion Criteria	X															X	
Enrollment	X																
Demographics	X																
Diagnosis	X																
Medical History ^b	X	X	X	X	X	X	X	X	X	X	X	X	X	X	X	X	
Vital Signs	X	X	X	X	X	X	X	X	X	X	X	X	X	X	X	X	
Physical Examination ^c	X	X	X	X	X	X	X	X	X	X	X	X	X	X	X	X	
Medications	X	X	X	X	X	X	X	X	X	X	X	X	X	X	X	X	
ECOG	X	X	X	X	X	X	X	X	X	X	X	X	X	X	X	X	
Toxicity / AE assessment		X	X	X	X	X	X	X	X	X	X	X	X	X	X	X	
Con Med assessment		X	X	X	X	X	X	X	X	X	X	X	X	X	X	X	
Blood tests ^d	X	X	X	X	X	X	X	X	X	X	X	X	X	X	X	X	
Troponin, BNP, CK-MB	X													X			
EPO level	X					X				X				X			
Pregnancy test	X																
Electrocardiogram (EKG) ^e	X	e	e	e	e	e	e	e	e	e	e	e	e	e	e	e	

End of Tier 1 – Patients meeting composite response and toxicity endpoint may continue to accrue

Echocardiography with Doppler ^f	X																								
Bone Marrow Aspirate and Biopsy	X																								X
Ultrasound (left upper quadrant)	X																								X
Research blood	X	X						X								X					X			X	
Research Bone Marrow	X																								X
Treatment Administration Form and Compliance assessment		X	X	X	X	X	X	X	X	X	X	X	X	X	X	X	X	X	X	X	X	X	X	X	
MPN-SAF form		X	X	X	X	X	X	X	X	X	X	X	X	X	X	X	X	X	X	X	X	X	X	X	
Record HgB level and HgB change ^g		X	X	X	X	X	X	X	X	X	X	X	X	X	X	X	X	X	X	X	X	X	X	X	
Record RBC transfusion history		X ^h	X	X	X	X	X	X	X	X	X	X	X	X	X	X	X	X	X	X	X	X	X	X	
Composite response and toxicity endpoint assessment																									X

a. Visits are weekly if there is a dose change (escalated or reduced or held for toxicity). Visits are biweekly if dose is maintained. Visits are extended to every 4 weeks (once per cycle) as long as dose is maintained for 4 weeks.

b. Must record baseline comorbidities, pre-existing symptoms

c. Spleen size should be recorded

d. Blood tests are: CBC, CMP, UA, Phosphorous, LDH

e. Electrocardiogram required at screening. Only required at subsequent visits in the event of a dose increase.

f. Echocardiogram or Cardiac MRI will be done once every 2 cycles (8 weeks or 56 days)

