g. Baseline HgB is defined as median HgB within 28 days of Cycle 1, Day 1

h. Include erythrocyte transfusion history 8 weeks prior to screening

Tier 2 Schedule of Assessments	Screening	Treatment Tier 2																						End of Tier2 p patients meeting composite response and toxicity endpoints may continue vactosertib		
		Cycle 1			Cycle 2			Cycle 3			Cycle 4			Cycle 5			Cycle 6									
	Pre-study D-28 to -1	Wk1 ^a	Wk2 ^a	Wk3 ^a	Wk4 ^a	Wk5 ^a	Wk6 ^a	Wk7 ^a	Wk8 ^a	Wk9 ^a	Wk10 ^a	Wk11 ^a	Wk12 ^a	Wk13 ^a	Wk14 ^a	Wk15 ^a	Wk16 ^a	Wk17 ^a	Wk18 ^a	Wk19 ^a	Wk20 ^a	Wk21 ^a	Wk22 ^a	Wk23 ^a	Wk24	
Informed Consent Form	X																									
Inclusion/Exclusion Criteria	X																									
Enrollment	X																									
Demographics	X																									
Diagnosis	X																									
Medical History ^b	X	X	X	X	X	X	X	X	X	X	X	X	X	X	X	X	X	X	X	X	X	X	X	X	X	
Vital Signs	X	X	X	X	X	X	X	X	X	X	X	X	X	X	X	X	X	X	X	X	X	X	X	X	X	
Physical Examination ^c	X	X	X	X	X	X	X	X	X	X	X	X	X	X	X	X	X	X	X	X	X	X	X	X	X	
Medications	X	X	X	X	X	X	X	X	X	X	X	X	X	X	X	X	X	X	X	X	X	X	X	X	X	
ECOG	X	X	X	X	X	X	X	X	X	X	X	X	X	X	X	X	X	X	X	X	X	X	X	X	X	
Toxicity / AE assessment	X	X	X	X	X	X	X	X	X	X	X	X	X	X	X	X	X	X	X	X	X	X	X	X	X	
Con Med assessment	X	X	X	X	X	X	X	X	X	X	X	X	X	X	X	X	X	X	X	X	X	X	X	X	X	
Blood tests ^d	X	X	X	X	X	X	X	X	X	X	X	X	X	X	X	X	X	X	X	X	X	X	X	X	X	
Troponin, BNP, CK-MB	X																									X
EPO level	X					X			X										X						X	
Pregnancy test	X																									
Electrocardiogram (EKG) ^e	X	e	e	e	e	e	e	e	e	e	e	e	e	e	e	e	e	e	e	e	e	e	e	e	e	
Echocardiography with Doppler ^f	X																									X
Bone Marrow Aspirate and Biopsy	X																									X
Ultrasound (left upper quadrant)	X																									X
Research blood	X	X				X			X										X						X	
Research Bone Marrow	X																									X
Treatment Administration Form and Compliance assessment		X	X	X	X	X	X	X	X	X	X	X	X	X	X	X	X	X	X	X	X	X	X	X	X	
MPN-SAF form		X	X	X	X	X	X	X	X	X	X	X	X	X	X	X	X	X	X	X	X	X	X	X	X	

*Patients who have completed Tier 1 would not require repeat assessments if done within 28 days of Tier 2 enrollment

- a. Visits are weekly if there is a dose change (escalated or reduced or held for toxicity). Visits are biweekly if dose is maintained. Visits are extended to every 4 weeks (once per cycle) as long as dose is maintained for 4 weeks.
- b. Must record baseline comorbidities, pre-existing symptoms
- c. Spleen size should be recorded

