6.3. Treatment Phase

6.3.1. Cycle 1, Day 1 (D0) Testing and Procedures:

- 6.3.1.1. 6.3.1.1. Pre-dose evaluation:History and Physical Exam
- 6.3.1.2. Record palpated Spleen size
- 6.3.1.3. Laboratory Testing
 - CBC
 - CMP
 - Uric Acid
 - Phosphorus
 - LDH
- 6.3.1.4. Establish and Record Baseline Hemoglobin: Baseline Hemoglobin is defined as the median hemoglobin within 28 days of Cycle 1, Day 1 (D0).
- 6.3.1.5. EKG (QTc) in the event of a dose increase
- 6.3.1.6. Complete MPN-SAF-TSS Myeloproliferative symptom assessment form total symptom score)³³ (Appendix A)
- 6.3.1.7. Record baseline co-morbidities and pre-existing symptoms.

- 6.3.1.2. Dispense study drug (vactosertib 50 mg tabs, #130) for cycle from research pharmacy and deliver to eligible subject during clinic visit.
- 6.3.1.3. Starting dose for Tier 1 is DL1. Subject will receive the one dose of vactosertib (DL1) under supervision of treating physician or research study nurse.
- 6.3.1.4. Research blood sample (20mL) will be collected either with SOC labs (if they are on a stable dose of vactosertib) or one hour after vactosertib dose (if dose of vactosertib is modified).
- 6.3.1.5. Subject will return for Follow-up Testing and Procedures (section 6.3.2) in 7 (\pm 2) days after first dose of vactosertib.

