10.1.3 Erythropoietic Response

Defined by any of the following:

- HGB increase of 1.5g/dL compared to baseline HGB;
- Reduction in PRBC transfusion rate to $\leq 50\%$ of pre-treatment transfusion rate; or
- Reduction in PRBC transfusions by ≥ 4 Units over an 8-week period.

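### The pre-treatment transfusion rate behind erythropoietic response is not dated, and the only window the plan states stops at screening, up to 28 days before the first dose

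*Combined protocol and SAP*

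**What the plan says.** - **Response rule.** Section 10.1.3 has two transfusion limbs. One is a fall to half or less "of pre-treatment transfusion rate"; the other is a fall of at least 4 units over 8 weeks. Neither limb dates its comparison period.
- **History collected.** Section 6.2.2.10 asks for "Recording of Transfusion History for the two months (8 weeks) prior to screening". Footnote h of the schedule in section 6.1 says "Include erythrocyte transfusion history 8 weeks prior to screening". In the Tier 1 table that footnote is attached to the Week 1 cell of the row "Record RBC transfusion history".
- **Gap to dosing.** Section 6.2 says "subjects will begin vactosertib (DL1) within 28 days of screening".
- **On-study recording.** Section 6.3.2 records an interval PRBC volume at follow-up visits and does not say when the first interval starts. The C1D1 list in section 6.3.1 has no transfusion item.
- **Hemoglobin limb, for contrast.** Section 6.3.1 says "Baseline Hemoglobin is defined as the median hemoglobin within 28 days of Cycle 1, Day 1 (D0)". The note to Table 3 places it in the 4 weeks before the first treatment day.
- **Entry.** Section 4.2 accepts hemoglobin below 10 g/dL or, alternatively, "transfusion of ≥ 2 packed red blood cell (PRBC) unit within the past 4 weeks" with hemoglobin at or below 8.5 g/dL. The date from which the 4 weeks are counted is not given.

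**The concern.** A reduction in transfusion means something only relative to a dated baseline. Here the stated history can end four weeks before treatment begins. Units given in those weeks could go into the baseline, into the first on-study interval, or nowhere, and two abstractors could reasonably differ.

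The hemoglobin limb of the same endpoint is tied to C1D1, so a baseline that reaches the first dose was feasible.

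Erythropoietic response feeds the composite in Table 5. That composite decides whether Tier 2 opens and whether vactosertib is judged worth developing. The trial has one arm, so no control group would show the same artefact and let it be subtracted.

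**Working it through.** **The plan's own figure.** The plan gives no number for the transfusion baseline. The design that uses the endpoint (Table 4: at least 1 of 12, then at least 4 of 37) does reproduce. P(go | p) is the sum over x from 1 to 12 of P(X1 = x | 12, p) × P(X2 ≥ 4 − x | 25, p). This gives 0.0935 at p = 0.05 and 0.902 at p = 0.20, as the plan claims. The issue is how a responder is counted, not the design arithmetic.

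**What the gap can do to one patient.** Take a steady 2 units per 4 weeks (assumed). The 8-week baseline is 4 units and a 28-day gap holds 2 more. Suppose the drug halves need, so the first 8 weeks on study hold 2 units. Since 2 ≤ 0.5 × 4, this is a response. If the 2 gap units are put into the first interval, the count is 4, which exceeds 2, and the response is lost. This error works against the drug.

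**Noise.** Let need be λ units per 4 weeks, Poisson. The 8-week count has variance 2λ. Twelve weeks scaled to 8 has variance (8/12)² × 3λ = 1.33λ, one third less.

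**Simulation with no drug effect.** All inputs except the response rule and the 28-day maximum are assumptions.
- A and B are the two 4-week blocks before screening, each Poisson(λ).
- C is the 4 weeks from screening to C1D1, Poisson(kλ).
- O is the first 8 weeks on study, Poisson(2kλ).
- k = 1 is stable need; k = 0.7 or 1.3 is a 30% fall or rise from screening.
- λ has mean 2 or 3, with between-patient CV 0 or 0.5 (gamma).
- Any patient with at least one unit in A + B is kept.
- Response is O ≤ 0.5b or b − O ≥ 4. The baseline b is either A + B, or (A + B + C) × 8/12.
- There are 1,000,000 patients per scenario.

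| Need from screening | Mean λ, CV | Baseline A + B | Gap weeks added | Reduction (points) |
|---|---|---|---|---|
| Stable | 2, 0 | 22.9% | 20.6% | 2.3 |
| Stable | 2, 0.5 | 26.4% | 23.5% | 2.9 |
| Stable | 3, 0 | 18.6% | 15.3% | 3.3 |
| Stable | 3, 0.5 | 22.8% | 19.6% | 3.2 |
| Falls 30% | 2, 0 | 41.5% | 35.0% | 6.5 |
| Falls 30% | 2, 0.5 | 44.5% | 37.3% | 7.2 |
| Falls 30% | 3, 0 | 38.1% | 29.6% | 8.5 |
| Falls 30% | 3, 0.5 | 42.8% | 33.8% | 9.0 |
| Rises 30% | 2, 0 | 11.8% | 12.0% | −0.2 |
| Rises 30% | 2, 0.5 | 15.3% | 15.3% | 0.0 |
| Rises 30% | 3, 0 | 8.5% | 8.3% | 0.2 |
| Rises 30% | 3, 0.5 | 11.4% | 11.6% | −0.2 |

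Most of the false response in the stable rows remains after the change. It is count noise in the 50% criterion.

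**Cost in true response, stable need.** With the drug halving need, the longer baseline loses 1.2 to 1.7 points (for example 58.7% to 57.5% at mean 2, CV 0). With a 70% or 80% reduction in need, the change is between a loss of 0.4 and a gain of 0.9 points.

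**The case against.** **The gap may be captured already.** The Week 1 row asks for transfusion history, and footnote h says to include the earlier 8 weeks, which need not be the limit of the record. This stands, and a reader should not conclude that the plan omits the gap weeks. But no text requires them to be recorded, and recording them would still not say whether they count as baseline or as treatment.

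**Selection.** A reader might infer that the baseline is inflated for transfused patients generally, because entry can require 2 units in 4 weeks that overlap the baseline. If every patient must have at least 2 units in the 4 weeks before screening, the simulated baseline is indeed 4.9–5.6 units against a true 4.0–4.8 per 8 weeks (mean need 2). False response is then 22–30% as written and 17–25% with the gap added (mean need 2–3). Section 4.2 does not impose that condition. A current hemoglobin at or below 8.5 already satisfies the limb of below 10. The transfusion limb decides entry only if the 8.5 is an earlier value and the current one is 10 or more. The 4 weeks also have no reference date: counted back from C1D1 after a full 28-day gap, they would not touch the baseline at all. Inflation is therefore conditional and probably confined to a small subgroup.

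**Direction.** It is also tempting to say that the window credits vactosertib with falls that came before it. That holds if need is falling. If need is rising, the older window understates the baseline and hides responses. The documents support neither trend.

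**Model limits.** The 28-day gap is a maximum, and the model uses one 8-week look. Repeated looks would raise false response. The requirement in section 12.2.2 that benefit last 8 weeks without DLT could lower it.

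**Conclusion.** The point holds as a defect of definition with a modest statistical cost. The pre-treatment rate has no dates, the only stated window can end 28 days before dosing, and the start of the on-study count is not fixed. The baseline may be out of date in either direction and uses fewer weeks than are available.

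Among transfused patients, the gain from adding the gap weeks is about 2 to 3.5 points of false response when need is stable, about 6 to 9 if it falls 30% and about 0 if it rises 30%. These figures rest on assumed Poisson need of 2–3 units per 4 weeks, a full 28-day gap and no drug effect.

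A reader might go on to a type I error for the go decision well above the plan's 10%. That needs the transfused share, the transfusion rates and the response rate in everyone else. The plan gives none of these, so no trial-level figure can be derived. Severity: minor; a cheap improvement.

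**What to change.** Make the same edit in section 6.2.2.10, footnote h of the schedule and section 10.1.3:
- Record every PRBC unit from 8 weeks before screening to the day before C1D1.
- Define the pre-treatment rate as those units divided by the actual number of weeks (8 to 12), scaled to 8 weeks, and use it for both transfusion limbs.
- Start the on-study count at C1D1.

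Extending the window is better than sliding the same 8 weeks forward to end at C1D1. With stable need, sliding leaves false response essentially unchanged (22.7% against 22.9% at mean 2, CV 0), because it adds no weeks. Extending also dilutes any selection in the subgroup that enters on transfusion.

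The cost is wording in three places, a transfusion check at C1D1, a baseline window that differs between patients, and possibly a slightly lower observed response rate.

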6.3. Treatment Phase

6.3.1. Cycle 1, Day 1 (D0) Testing and Procedures:

- 6.3.1.1. 6.3.1.1. Pre-dose evaluation:History and Physical Exam
- 6.3.1.2. Record palpated Spleen size
- 6.3.1.3. Laboratory Testing
 - CBC
 - CMP
 - Uric Acid
 - Phosphorus
 - LDH
- 6.3.1.4. Establish and Record Baseline Hemoglobin: Baseline Hemoglobin is defined as the median hemoglobin within 28 days of Cycle 1, Day 1 (D0).
- 6.3.1.5. EKG (QTc) in the event of a dose increase
- 6.3.1.6. Complete MPN-SAF-TSS Myeloproliferative symptom assessment form total symptom score)³³ (Appendix A)
- 6.3.1.7. Record baseline co-morbidities and pre-existing symptoms.

- 6.3.1.2. Dispense study drug (vactosertib 50 mg tabs, #130) for cycle from research pharmacy and deliver to eligible subject during clinic visit.
- 6.3.1.3. Starting dose for Tier 1 is DL1. Subject will receive the one dose of vactosertib (DL1) under supervision of treating physician or research study nurse.
- 6.3.1.4. Research blood sample (20mL) will be collected either with SOC labs (if they are on a stable dose of vactosertib) or one hour after vactosertib dose (if dose of vactosertib is modified).
- 6.3.1.5. Subject will return for Follow-up Testing and Procedures (section 6.3.2) in 7 (\pm 2) days after first dose of vactosertib.

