6.3.2.3. Dose Adjustment Testing and Procedures (*section 6.3.2.2*)

6.3.2.4. If Day 1 of Cycle,

- Pill Counts to assess compliance (subjects return all vials at visit for pill counts).
- Dispense study drug (vactosertib 50 mg tabs) for one cycle from research pharmacy and deliver to subject during clinic visit.
- Research blood sample (20mL) will be collected one hour after vactosertib dose (also collected on C1D8).

6.3.3. **Dose Adjustment Decision** ([see Table 3 section 7](#))

6.3.3.1. **Escalate** to next dose level

- Subject will receive one dose of vactosertib at escalated dose level under supervision of treating physician or research study nurse.
- Research blood sample (20mL) will be collected approximately 1hr after escalated dose taken.
- If dose is at maximum level (DL4), and patient has at least stable disease, then patient can remain on study at maximum level (DL4).
- If dose is at maximum level (DL4), and patient has progressive disease, then patient will be removed from study.
- Subject will return for Follow-up Testing and Procedures in 7 (\pm 2) days from start of new dose level.

6.3.3.2. **Maintain** current dose level

6.3.3.2.1. **New Maintain Decision:**

- Subject will return for Follow-up Testing and Procedures in 14 (\pm 3) days.

6.3.3.2.2. **Ongoing Maintain Decision:**

- After at least two, consecutive Maintain dose-adjustment decision at the same dose level, subject will return for Follow-up Testing and Procedures no later than Day 1 of the next cycle of vactosertib.

6.3.3.3. **Hold** vactosertib

- If last dose received is at minimum dose level (DL0), patient will be removed from study. Otherwise:

6.3.3.3.1. **New Hold Decision**

- Subject will return for Follow-up Testing and Procedures in 7 (\pm 2) days.

6.3.3.3.2. **Ongoing Hold Decision**

- If dose is held > 28 days, subject will be removed from study.
- If dose is held < 28 days, subject will return for Follow-up Testing and Procedures in 7 (\pm 2) days

6.3.3.4. **Restart** vactosertib

- Vactosertib dose will be reduced to one dose level lower than the last dose level received.
- If last dose received was at minimum dose level (DL0), patient should have already been removed from study.
- Subject will return for Follow-up Testing and Procedures in 7 (\pm 2) days from start of new dose level.
- Subject will receive one dose of vactosertib at restarted dose level under supervision of treating physician or research study nurse.

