- Research blood sample (20mL) cycle 1 will be collected approximately 1hr after dose taken.

6.3.4. **Additional Scheduled Studies and Procedures:**

Additional studies will be performed at regular intervals for all Subjects independent of the current dose of vactosertib; provided the indicated studies have not already been performed within 7 days.

6.3.4.1. Cardiac Evaluation after every three cycles is completed (every 84 \pm 7 days):

- Transthoracic Echocardiogram
- Cardiac troponin, BNP, CK-MB

6.3.4.2. Serum EPO is measured on Day 1 of each cycle (every 28 \pm 3 days).

6.3.4.3. Subjects will maintain a diary to record adverse events that occur between clinic visits (e.g., patient diaries).

6.3.5. **End of Tier Testing and Procedures:**

At the end of Cycle 4 (approximately Week 16 \pm 7 days), the following procedures will be performed for all Subjects.

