9.1. On-target Pharmacodynamic Response Reported by SMAD2/3 Phosphorylation

9.1.1. Collection of Specimen(s):

9.1.1.1. Blood specimens are collected at the following times:

9.1.1.1.1. Screening and at End of Tier Testing.

9.1.1.1.2. One hour after observed dose any time a new dose level is used (e.g., following a dose escalation, dose restart, dose reduction).

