9.1.1.2. Bone marrow Specimens

9.1.1.2.1. Bone marrow aspirate specimens are collected at Screening and at end of Cycle 4 (16 weeks ± 7 days). In the event of a dry tap, the requirement for the bone marrow aspirate is waived (a biopsy is still required).

9.1.1.2.2. Bone marrow biopsy sections will be obtained at Screening and at end of Cycle 4. Sections will be obtained from hematopathology after clinical evaluation is complete. Unstained, sections will be cut from the residual tissue block. No separate research specimen is required.

9.1.2. Handling of Specimens(s):

9.1.2.1. Blood specimens are collected in standard EDTA (purple top) vacutainer tubes.

9.1.2.2. Bone marrow aspirate specimens will be collected into heparinized syringes and transferred to standard heparin (green top) vacutainer tubes.

9.1.2.3. Bone marrow biopsy sections will be obtained from Weill Cornell Medicine hematopathology director [name], PhD.

9.1.3. Shipping of Specimen(s): Specimens will be hand-delivered to the [name] Lab.

9.2. Molecular Response Reported by JAK2V617F, CALR type 1 or type 2, MPLW515L/K Driver Mutation Variant Allele Frequency

9.2.1. Collection of Specimen(s):

9.2.1.1. Blood specimens are collected at Screening, at end of Cycle 4 (16 weeks ± 7 days) and at End of Tier Test.

9.2.1.2. Bone marrow aspirate specimens are collected at Screening and at end of Cycle 4.

9.2.1.3. Bone marrow biopsy sections will be obtained from hematopathology after clinical evaluation is complete. Unstained, sections will be cut from the residual tissue block. No separate research specimen is required.

9.2.2. Handling of Specimens(s):

9.2.2.1. Blood specimens are collected in standard EDTA (purple top) vacutainer tubes.

9.2.2.2. Bone marrow aspirate specimens will be collected into heparinized syringes and transferred to standard heparin (green top) vacutainer tubes.

9.2.3. Shipping of Specimen(s): Specimens will be hand-delivered to [name] Lab.

10. Measurement of Effect

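### The plan's timing rules for research blood conflict for stable-dose patients, and the End of Tier blood and end-of-Cycle-4 marrow have none, so the pSMAD2/3 endpoint can mix on-drug and off-drug samples

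*Combined protocol and SAP*

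**What the plan says.** All places are in the combined protocol and SAP.

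- **Section 6.3.1, research-blood item (the second item numbered 6.3.1.4).** Research blood "will be collected either with SOC labs (if they are on a stable dose of vactosertib) or one hour after vactosertib dose", the latter if the dose is modified. The stable-dose branch gives no time since dose.
- **Section 6.3.2.4, Day 1 of later cycles.** "Research blood sample (20mL) will be collected one hour after vactosertib dose (also collected on C1D8"). There is no stable-dose exception.
- **Section 6.3.3.1, escalation.** "Research blood sample (20mL) will be collected approximately 1hr after escalated dose taken".
- **Section 6.3.3.4, restart.** The sample "will be collected approximately 1hr after dose taken".
- **Section 9.1.1.1, pSMAD2/3 blood.** Two kinds of draw are listed: "Screening and at End of Tier Testing", with no post-dose time, and "One hour after observed dose any time a new dose level is used (e.g., following a dose escalation, dose restart, dose reduction"). A draw with routine labs is not among them.
- **Section 9.1.1.2, marrow.** "Bone marrow aspirate specimens are collected at Screening and at end of Cycle 4 (16 weeks ± 7 days"), again with no time since dose. Section 6.3.6.6 waives an End of Tier marrow in Tier 2, so by the text this is the only scheduled on-treatment marrow in either tier.
- **Section 6.2.2.9.** The research specimens are "for pSMAD and VAF quantification".

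Section 12.4.2.3 counts any reduction in pSMAD2/3 staining, in marrow sections or in blood or marrow cells, as a pharmacodynamic response. It names no sample or time point. Section 2.5.1 plans to correlate pSMAD2/3 with clinical endpoints.

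**The concern.** pSMAD2/3 is the plan's measure of whether the drug is inhibiting its target. Vactosertib is cleared within hours and is given five days on, two days off. A sample taken one hour after a dose and a sample taken before a dose, or on an off-day, therefore reflect different exposure. If both enter one endpoint, a sample without reduction may mean either that the target was not inhibited or that no drug was present at the draw.

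The plan permits this in two ways. First, if the stable-dose branch of section 6.3.1.4 is carried to later visits, it contradicts section 6.3.2.4. Section 6.3.2.1 lists the follow-up laboratory tests under the pre-dose evaluation, so a draw with routine labs may well be pre-dose. Second, the End of Tier blood and the end-of-Cycle-4 marrow have no timing rule anywhere, and they are the end-of-treatment samples most naturally compared with screening. No section requires time since last dose to be recorded with the sample, so the states cannot reliably be separated afterwards.

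**Working it through.** The plan states no sample size, power or error rate for this endpoint, so there is no design figure to reproduce. The check has two parts.

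**1. Timing rules side by side**

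| Sample | Time since dose | Source |
|---|---|---|
| Stable dose, under C1D1 | None (routine labs) | 6.3.1.4 |
| Day 1 of later cycles; C1D8 | 1 h | 6.3.2.4 |
| Escalation | About 1 h | 6.3.3.1 |
| Restart | About 1 h | 6.3.3.4 |
| Any new dose level | 1 h after an observed dose | 9.1.1.1 |
| End of Tier blood | None | 6.3.5.7, 9.1.1.1 |
| End-of-Cycle-4 marrow | None (±7 days) | 9.1.1.2 |

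**2. Plasma drug left at an untimed draw**

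Inputs:
- Half-lives: the Table 1 averages run from 1.69 to 5.71 h on Day 1 and from 1.71 to 6.92 h on Day 5. The MDS values in Table 2 run from 2.0 to 2.8 h. The text of section 2.2.1 gives averages of 1.86 to 5.47 h after the first dose and a range of 0.4 to 18.1 h after repeated dosing. The first-dose text range does not match the Day 1 row of Table 1, but both mean a few hours.
- Schedule: twice daily, 5 days on and 2 off (section 7.7), so off-days are 2/7 = 28.6% of days.
- Assumption: about 60 h from the evening dose on day 5 to the morning of day 8 (12 h + 48 h).
- Assumption: single-exponential decline, fraction left = 0.5^(t / half-life). The protocol describes the decline as multi-exponential, so the results are approximate.

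| Half-life | 1 h | 12 h | 24 h | 60 h |
|---|---|---|---|---|
| 1.69 h (shortest average) | 66% | 0.73% | 0.005% | <0.001% |
| 2.0 h (MDS, low) | 71% | 1.6% | 0.02% | <0.001% |
| 2.8 h (MDS, high) | 78% | 5.1% | 0.26% | <0.001% |
| 6.92 h (longest average) | 90% | 30% | 9.0% | 0.25% |
| 18.1 h (extreme in text) | 96% | 63% | 40% | 10% |

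For example, 0.5^(60/6.92) = 0.25% and 0.5^(60/18.1) = 10%.

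**Where such draws fall.** A 28-day cycle is four 7-day weeks. If Day 1 opens a 5-day block, Days 22–26 are dosing days and Days 27–28 are off. A pre-dose draw on Day 1 of the next cycle then follows two off-days (the 60 h column), and the nominal end of Cycle 4 is itself an off-day. By contrast, Table 1 puts median time to peak at about 0.5 to 1.8 h, so the one-hour draws lie near peak.

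**The case against.** A reader might infer that on-treatment pSMAD2/3 samples in general may be drawn at any time. The documents do not support that. Sections 6.3.2.4, 6.3.3.1, 6.3.3.4 and 9.1.1.1 fix about one hour post-dose for Day 1 of later cycles, C1D8, escalation, restart and any new dose level. The routine-labs clause sits under C1D1, when a new patient takes the first dose and cannot yet be on a stable one. It matters only if carried to later visits, or for Tier 1 completers entering Tier 2, whom a footnote to the Tier 2 schedule contemplates. This stands, and it confines the point to that clause and the two untimed sample types.

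A reader might also infer that responders are selectively mistimed, biasing the link between inhibition and benefit toward zero. That is not shown. Patients on a stable dose are not only adequate responders: section 6.3.3.1 keeps patients with at least stable disease at the highest dose level, and under Table 3 the dose is maintained whenever neither the escalation nor the hold criteria are met. The End of Tier blood and the marrow are planned regardless of response. If timing did differ by response, the association could be distorted in either direction.

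The endpoint is secondary and descriptive, with no formal test, and enters neither the two-stage rule nor the composite endpoint. On its wording a reduction in a one-hour sample can qualify, and a later drug-free sample need not cancel it. Finally, plasma half-life is not the recovery time of pSMAD2/3. All of this limits the consequence. None of it removes the contradiction or supplies the missing timing rules.

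**Conclusion.** The point holds as a contradiction plus a gap. Section 6.3.1.4 conflicts with section 6.3.2.4 for stable-dose patients and has no counterpart in section 9.1.1.1. The End of Tier blood and the only scheduled on-treatment marrow have no time-since-dose rule. Followed as written, the plan can yield nearly drug-free samples: at 60 h, at most 0.25% of plasma drug remains for the tabulated average half-lives and about 10% at the 18.1 h extreme. This rests on single-exponential decline and on cycles that open with a dosing block.

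The descriptive pSMAD2/3 endpoint and its planned correlation with clinical endpoints can therefore mix exposure states. Neither the size nor the direction of the effect can be computed, because the documents do not give the duration of pSMAD2/3 suppression. It would go too far to conclude that the endpoint is uninterpretable, since most of the blood sampling is timed. No sample size, power, error rate or go/no-go decision changes. The correction is worth making before samples are taken, because an untimed sample cannot be repaired later.

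**What to change.** - Reconcile section 6.3.1.4 with sections 6.3.2.4 and 9.1.1.1, so that on-treatment pSMAD2/3 blood uses the one-hour post-dose window already stated.
- Book the End of Tier blood and the week-16 marrow on an already planned dosing day within the existing visit window, adding no dose. With Day 1 opening a block, Day 26 is the last dosing day of a cycle, two days before its nominal end and inside ±7 days. Section 6.3.6.6 places Tier 2 testing after the sixth cycle is completed, so it should say whether the same window applies.
- Record time since last dose with every research sample.
- Name in section 12.4.2.3 the sample or samples that define pharmacodynamic response.
- Report samples outside the window separately, including those from patients on a dose hold, and do not discard them.

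The cost is a one-hour wait at some visits, tighter scheduling within the window, and one data field. No extra samples are needed.
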